15. DATA/SAMPLE STORAGE FOR FUTURE USE

Study coordination, database management and statistical analysis will be performed by the Clinical Cardiovascular Research Center (CCRC) at the University of Rochester Medical Center (U of R) acting as the Coordinating Center for the study.

Data will be captured using TrialMaster, a HIPAA compliant secure web-based electronic data capture (EDC) system that is used to support the clinical research process. Data that are entered are validated against a set of rules to ensure the accuracy of the clinical data. The TrialMaster system is housed on CCRC servers that are housed behind the U of R firewall in

the U of R Primary Data Center, where physical access and environmental controls are in place to protect the data. All access to the data is through an authentication process provided by the system and over the encrypted, secured U of R network, which both provide the necessary controls to prohibit unauthorized access to the clinical data. Continuous availability of the data is provided by mirroring the databases to servers located in a physically separate Secondary Data Center. Additional details are in the Data Safety Monitoring section below.

Only enrolling site personnel authorized by the site Principal Investigator will have access to the EDC system. Study personnel at each site delegated with EDC permission will be required to complete EDC training before receiving access to the system. Site personnel with EDC permission will have access to the system 24/7 for data entry. Study personnel will initially enter all data related to the randomization and baseline data collection and will then complete data entry after each identified data collection timeframe per Table 1.

Data collected may be used for the development of future research studies. We will maintain the confidentiality of the data throughout the process. Only authorized research personnel working on the project will have access to the data.

16. DATA AND SAFETY MONITORING PLAN

Adverse Event Data

An adverse event is any unexpected symptom, sign, illness, or experience that develops or worsens during the course of the study and is possibly or definitely related to study procedures. All protocol-defined adverse events will be collected after subject randomization at all subject contacts as indicated in Table 1. Adverse event data will be captured in the electronic data capture system and investigators are responsible for reporting to and following local Institutional Review Board (IRB) guidelines.

Adverse Event Reporting

Investigators shall report to their local IRB per local reporting guidelines, and report in the electronic data collection system within five business days of PI awareness only real or suspected, serious and unanticipated adverse events that are related to participation in the study. Events related to standard of care such as medications side effects do not need to be reported unless severe as defined below. Death of a subject must be reported as an adverse event, per the serious adverse event definition below. The PI is aware that investigators are responsible for reporting to and following the guidance of any other applicable oversight bodies, including the Institutional Review Board (IRB).

The CDC will be forwarding relevant documents to the Chair of DSMB for review and the Chair will determine whether individual case will require immediate assessment by the full DSMB committee or it could be assessed during electively scheduled DSMB meeting. The main point of assessment by DSMB will be to judge whether given adverse event could be related to ablation.

Serious Adverse Event Definition

This population is at increased risk of heart failure, death, and poor clinical outcomes. A serious adverse event (SAE) is defined as any adverse medical experience that results in any of the following outcomes:

- death;
- is life-threatening;
- requires inpatient hospitalization or prolongation of existing hospitalization;
- results in permanent impairment of a body structure or a body function;
- requires medical or surgical intervention to prevent permanent impairment or damage;
- leads to fetal distress, fetal death or a congenital abnormality or birth defect.

Data Safety Monitoring Board

A data and safety monitoring board (DSMB) will be convened to independently monitor the conduct and the outcomes of the trial. The DSMB will be responsible for monitoring the safety and well-being of the patients participating in this study and ensuring the ethical conduct of the trial. The DSMB will be responsible for safeguarding the interests of study participants, assessing the safety and efficacy of study procedures, and for monitoring the overall conduct of the study. The DSMB will be an independent group advisory to the study principal investigator and will be asked to provide recommendations about starting, continuing, and stopping the study. In addition, the DSMB is asked to make recommendations, as appropriate, about:

- Efficacy of the study intervention
- Benefit/risk ratio of procedures and participant burden
- Selection, recruitment, and retention of participants
- Adherence to protocol requirements
- Completeness, quality, and analysis of measurements
- Amendments to the study protocol and consent forms
- Performance of individual centers and core labs
- Participant safety
- Notification of and referral for abnormal findings

Data on clinical events including procedural complications, hospitalizations, stroke, atrial tachyarrhythmias, and death will also be collected by the study and provided to DSMB for evaluation of risks associated with ablation in the study participants.

The board will be comprised of 3 independent members: (1) 1 statistician with experience in clinical trials; (2) 1 cardiologist with expertise in clinical trials; and (3) 1 electrophysiologist with expertise in ablation.

The DSMB will meet before trial commencement and 3 times after each group of 30 patients

is enrolled. It is anticipated that these meetings will take place via conference call. One of the clinical cardiologists will be selected to chair the committee and will serve as the principal representative of the group. The Chair of the committee will be informed monthly about adverse events and will monitor safety of the patients during interim time between formal meetings of DSMB.

Monthly reports will be sent by the CDC to the DSMB chair, to report data on expected and unexpected adverse events. The Chair of the DSMB will have the right to convene additional meetings with all DSMB members when needed. The DSMB will carefully consider if these events are consistent with anticipated clinical outcome, i.e. unrelated, or a consequence of the study procedure, i.e. related. Information on all these events will be sent to DSMB Chair on monthly basis and in addition, a full DSMB report will be prepared before every elective DSMB meeting.

Adverse events that will be judged by the DSMB Committee as related to repeat ablation will be described and reported to CDC IRB at University of Rochester as well as local IRBs.

17. DATA ANALYSIS PLAN

For the primary endpoint of AF burden, i.e. percentage of overall follow-up spent by the subject experiencing atrial arrhythmias, the Wilcoxon rank-sum test will be used to statistically compare the conventional group vs. the active treatment group.

For the secondary composite end point, we will perform longitudinal event-free survival analysis, defined by survival and freedom from atrial arrhythmias, re-ablation, and cardiac hospitalization. Event-free survival rates, as captured by the composite secondary endpoint, will be displayed using the method of Kaplan-Meier. We will use the log-rank test to non-parametrically compare the overall survival curves for the two treatments. The other secondary endpoints of atrial flutter/tachycardia recurrence, repeat ablation incidence, and major adverse events will be compared utilizing negative binomial regression tests to statistically compare the event rates in the two arms, using the natural log of follow-up time as an offset. Quality of life measures will be compared between the arms using the non-parametric Wilcoxon rank-sum test.

The estimate for the sample size necessary to compare AF burden at 12 months between the conventional AF management arm vs. the Bio-Monitor 3-guided repeat ablation arm will assume a 1:1 distribution of subjects between the two arms. Since most of the re-ablation procedures will be carried out based on ICM-detected subclinical AF recurrences, we conservatively expect a re-ablation rate of 50% in the intervention arm vs. 5% in the conventional arm (in which only clinical episodes will be treated and resumption of antiarrhythmic medical therapy is also allowed).

For the planned analysis of the primary end point of AF burden involving the Wilcoxon rank-sum test, a two-sided $\alpha = 0.05$ and power of 80% was assumed. Based on our preliminary data and our prior studies on AF burden (The HARMONY Trial, Circulation Arrhythmia and Electrophysiology, 2015), the 12 month primary outcome of AF burden is assumed to be 25% vs. 16% in the conventional group, with a standard deviation of 15% (a conservative estimate which allows for 10% drop-out). A reduction from 25% to 16% and 80% power,

with a drop-out rate of 10%, will result in a total sample of 90 patients.

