Hybrid Ablation Plus Medical Therapy for Persistent Atrial Fibrillation
(HYBRID-AF)

ClinicalTrials.gov ID: **NCT04190186**

March 03, 2025

Statistical Analysis Plan for the HYBRID-AF Trial

1. Introduction This Statistical Analysis Plan (SAP) outlines the planned statistical analyses for the HYBRID-AF Trial, which has concluded.

2. Study Objectives The HYBRID-AF Trial evaluates the effectiveness of Biotronik ICM-guided intervention in reducing atrial fibrillation (AF) burden in patients with symptomatic persistent AF post-ablation. The primary objective is to compare AF burden between months 3 and 15 post-ablation between the Biotronik ICM-guided arm and the conventional AF management arm.

3. Study Design

- Randomized, controlled trial with 90 subjects assigned 1:1 to either conventional AF management or Biotronik ICM-guided management.
- Follow-up assessments at 3, 6, 9, 12, and 15 months post-randomization.
- Primary and secondary endpoints will be analyzed according to the intent-to-treat (ITT) principle.

4. Endpoints

Primary Endpoint:

- AF burden, defined as the percentage of time a subject experiences AF between months 3 and 15 post-ablation, measured by the Biotronik ICM.

Secondary Endpoints:

1. Composite endpoint of:
 - Clinically significant (>30 min) atrial arrhythmia (AF, atrial flutter, or atrial tachycardia) detected by Biotronik ICM post-index ablation.
 - Symptomatic AF recurrence (any duration).
 - Repeat AF ablation.
 - Cardiac hospitalization.
 - Death.
 - Healthcare utilization (hospitalization, ED visits, unplanned office visits).
2. Incidence of atrial flutter or tachycardia post-ablation.
3. Incidence of repeat procedures.
4. Major adverse events requiring rehospitalization.
5. Quality of life (QOL) assessment.

5. Sample Size Justification Based on prior studies and preliminary data, AF burden is expected to be 25% in the conventional group and 16% in the intervention group, with a standard deviation of 15%. A Wilcoxon rank-sum test at a two-sided alpha level of 0.05 and 80% power determined that 90 subjects (with a 10% dropout rate) were required.

6. Statistical Methods

Primary Analysis:

- AF burden comparison between groups using the Wilcoxon rank-sum test.
- Descriptive statistics for median and interquartile range (IQR) of AF burden.
- Sensitivity analysis for missing data using multiple imputation.

Secondary Analyses:

- Kaplan-Meier survival analysis for time to first atrial arrhythmia event.

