- Cox proportional hazards regression for risk factors associated with AF recurrence.
- Poisson regression for healthcare utilization.
- Mixed-effects models for QOL changes over time.

Subgroup Analyses:

- Stratification by baseline AF burden, age, and sex.
- Sensitivity analysis excluding early dropout subjects.

7. Data Handling

- All analyses will follow an ITT approach.
- Missing data will be addressed using multiple imputation and sensitivity analyses.
- Data management will be conducted per Good Clinical Practice (GCP) guidelines.

8. Reporting and Interpretation

- All results will be reported with 95% confidence intervals and p-values.
- Statistical significance is defined as $p < 0.05$.
- Study findings will be presented in accordance with CONSORT guidelines.

9. Conclusion This SAP ensures rigorous and transparent statistical analyses for the HYBRID-AF Trial, aligning with ClinicalTrials.gov reporting requirements.

Hybrid Ablation Plus Medical Therapy for Persistent Atrial Fibrillation

Lead Principal Investigator: [name]

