13. SUBJECT WITHDRAWALS

Subjects enrolled in the study may be withdrawn prior to the study completion for a variety of reasons including:

- Subject withdraws consent for any reason;
- Subject is lost to follow up despite best efforts to locate the subject;
- Subject is withdrawn at study investigator discretion.

Subjects may be considered lost to follow up after missing two consecutive follow-up visits with documented efforts to contact the subject.

These subjects will not undergo any additional study activities after withdrawal. If a subject becomes pregnant during the course of a study, they will continue to be monitored but no longer be part of the interventional arm. Data collection will occur until the date of withdrawal and utilized in the study analysis.

Patients who complete fewer than 3 months of follow-up and thus will not complete the blanking period will be excluded from primary end-point analysis, but will be included for all secondary end-points. Withdrawn subjects who have been randomized will not be replaced.

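### The stated 80% power for the Wilcoxon test at 90 subjects with 10% drop-out does not follow from the given inputs under a normal model, and its derivation is not documented

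*Combined protocol and SAP*

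**What the plan says.** SAP Section 5 takes AF burden as 25% in the conventional arm and 16% in the intervention arm, with SD 15%. It names the test and operating characteristics ("A Wilcoxon rank-sum test at a two-sided alpha level of 0.05 and 80% power") and concludes: "80% power determined that 90 subjects (with a 10% dropout rate) were required". There the SD and the drop-out rate are separate inputs.

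Protocol Section 17 uses the same figures but mentions the 10% in two places. It first describes a "standard deviation of 15% (a conservative estimate which allows for 10% drop-out" and then, in the next sentence, says that the design "with a drop-out rate of 10%, will result in a total sample of 90 patients". The SD before that allowance is not given.

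Three other provisions decide what drop-out costs the primary analysis:
- Protocol Section 13, on early withdrawals: "Patients who complete fewer than 3 months of follow-up and thus will not complete the blanking period will be excluded from primary end-point analysis". Withdrawn subjects are not replaced.
- Protocol Section 13, on later withdrawals: "Data collection will occur until the date of withdrawal and utilized in the study analysis".
- SAP Section 7: "Missing data will be addressed using multiple imputation and sensitivity analyses".

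The endpoint is a bounded percentage, "defined as the percentage of time a subject experiences AF between months 3 and 15 post-ablation" (SAP Section 4). Neither document states an outcome distribution, a sample-size formula or software, or the evaluable number behind 90.

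**The concern.** A reader will take 80% as the power of the planned Wilcoxon test after the planned drop-out. When the calculation is repeated with the stated inputs in the usual way, 90 appears before any drop-out inflation, and for a t-test. It is also unclear whether 90 is an evaluable or a randomised number, because the 10% stands once with the SD and once with the total.

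What is at stake is the accuracy of a stated design figure. The trial has concluded, and the planned analyses, estimates and confidence intervals do not depend on it.

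**Working it through.** **Inputs** (SAP Section 5, protocol Sections 4 and 17): difference 25 − 16 = 9 points, SD 15, two-sided alpha 0.05, power 80%, 1:1 allocation, 10% drop-out, 45 per arm. The standardised difference is 9/15 = 0.60. The sentence in Section 17 that gives both percentages is garbled as to arm, but the SAP settles it.

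**1. The plan's own figure, no drop-out, t-test or normal approximation**
- Normal approximation: n = 2(1.960 + 0.842)²/0.60² = 43.6, so 44 per arm, 88 in total.
- Exact two-sample t-test: 44.59, so 45 per arm, 90 in total, power 80.4%. This matches the stated number exactly.

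**2. The same calculations with 10% full loss**
- 88/0.9 = 97.8, so 98.
- 90/0.9 = 100.

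**3. Wilcoxon test under a normal shift.** Its efficiency relative to the t-test is 3/π = 0.955.

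| Route | Evaluable for 80% | Randomised with 10% loss |
|---|---|---|
| Normal approximation/0.955 | 45.7, so 46 per arm = 92 | 92/0.9 = 102.2, so 103 |
| Exact t/0.955 | 46.7, so 47 per arm = 94 | 94/0.9 = 104.4, so 105 (106 for equal arms) |
| Noether, P = Φ(0.60/√2) = 0.664 | (1.960 + 0.842)²/[12 × 0.25 × (P − 0.5)²] = 96.9, so 97 | 97/0.9 = 107.8, so 108 |

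Simulation (80,000 trials) gives 79.3% at 46 per arm and 80.1% at 47 per arm. One-sided versions with 10% loss give 78 to 86, so they do not return 90 either.

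**4. Power if 90 are randomised, normal model**

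| Evaluable | t-test | Wilcoxon (40,000 simulated trials) |
|---|---|---|
| 90, no loss | 80.4% | 78.1% |
| 86, about half of the 10% lost (an assumption) | not computed | 76.2% |
| 81, all of the 10% lost | 76.0% | 74.1% |

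The efficiency formula agrees: 78.5% at 90 and 74.0% at 81.

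**5. The 10% read as an allowance inside the SD only.** If SD 15 already carries the loss, all 90 are entered and Wilcoxon power is about 78%. Equivalently, if the allowance was a factor √0.9, the unpadded SD is 15 × √0.9 = 14.23. At that SD, 81 evaluable give 80.3% (t-test) and 78.6% (Wilcoxon). The gap is then 1 to 2 points.

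**6. Other shapes with the same means and SD, simulated Wilcoxon power**

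| Shape | 81 evaluable | 90 evaluable |
|---|---|---|
| Logistic shift | 79% | 83% |
| Beta | 87% | 90% |
| Beta, 10% zeros in each arm (assumed) | 80% | 84% |
| Beta, 20% zeros in each arm (assumed) | 76% | 80% |

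More extreme choices widen the range: at 81 evaluable, a uniform shift gives 71% and a gamma shape 92%.

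By formula, a logistic shift (efficiency π²/9 = 1.097) does return 90: 43.6/1.097 = 39.8, so 40 per arm; 40/0.9 = 44.4, so 45 per arm. Starting from the exact t size it gives 44.59/1.097 = 40.7, so 41, and 41/0.9 = 45.6, so 46 per arm or 92 in total. Simulated power at 40 per arm is 78.0%.

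The normal model is itself a poor description of a percentage: mean 16 with SD 15 puts Φ(−16/15) = 14.3% of that arm below zero, and mean 25 puts 4.8% there.

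**The case against.** The strongest reply has four parts.

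- **The documents do not assume normality.** They plan a rank test, and the SAP reports medians and IQRs. The normal model fits a bounded percentage poorly, and shapes that fit better straddle 80% at 81 evaluable. This stands. It rules out saying that 90 cannot be reproduced, since a logistic shift gives it by formula. It does not supply the missing derivation, because neither document names a logistic or any other shape.
- **The two mentions of 10% may be one allowance, restated in the summary sentence.** This also stands as a possible reading, and the normal-model gap is then only 1 to 2 points. A reader might infer that drop-out was counted twice in error; the text does not establish that. The wording still needs repair, because the unpadded SD is missing and the SAP presents SD 15% and 10% drop-out as separate inputs.
- **The 74% is a worst case.** It needs nine of the 90 subjects to give no primary-endpoint data. Section 13 excludes only those with under 3 months of follow-up and uses data up to withdrawal, and the SAP adds multiple imputation. This stands, so 74% should always carry that label.
- **The trial has concluded.** True, and it limits the consequence to the stated design figure.

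A reader might also infer from the exact match that a t-test calculation was used. The match is numerical only; neither document says so.

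**Conclusion.** The point holds as a minor one. Under the normal model, 80% Wilcoxon power at 90 subjects with 10% drop-out does not follow from the stated means and SD. Power is about 78% with no loss and about 74% in the worst case of full loss of 10%, a shortfall of about 2 to 6 points. If the SD is read as already padded, the shortfall is at the lower end.

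These figures rest on a normal shift with a common SD of 15. Confidence is high that the derivation is undocumented and the role of the 10% unclear. The true design power is not determined, because it depends on a distribution that the documents do not give.

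The tempting stronger conclusion, that the trial was underpowered, is not supported: logistic and bounded shapes with the same means and SD give about 76% to 87% at 81 evaluable, on both sides of 80%.

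**What to change.** In SAP Section 5 and protocol Section 17:

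1. Count drop-out once, either in N or in the SD. If in the SD, give the unpadded SD.
2. State the assumed distribution, the formula or software, and the evaluable N behind 90. If the sponsor holds the derivation and it returns 80%, supplying it settles the point.
3. Unless it does, restate the design power for the planned test, for example:

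> Under a normal-shift model, 90 subjects give about 78% power for the Wilcoxon test if all are analysed, and about 74% in the worst case that 10% contribute no primary-endpoint data. Power depends on the shape of the AF burden distribution and may be higher for a skewed outcome.

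Label this a correction of the design-stage calculation, so that it is not read as post-hoc power. The cost is a few sentences in each section. It requires no extra enrolment and no change to the data or the analysis.

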18. COORDINATING CENTER TRACKING

Acting as Coordinating Center for the study, in order to ensure all required information is provided to the Sponsor IRB, a Coordinating Center Tracking Spreadsheet will be submitted at the time of each annual progress review.

